3.3 Data Collection and Statistical Considerations

3.3.1 Sample Size Calculation:

It is anticipated that 90 children with PALF will be admitted to the clinical centers each year. Of those, approximately 20% will likely be due to acetaminophen overdose leaving 72 patients eligible for the study. We anticipate 25% of the eligible patients will not be enrolled, leaving an estimated 54 patients per year to be randomized. The one year death rate without transplant of 15% is lower than in the adult population. However, while a greater percentage of children receive a liver transplantation (40%), 40% of these children die, leaving an estimated overall survival with or without a liver transplant of 69% in the placebo arm. See diagram provided in Appendix 1 on page 20.

Based on these data, the estimated sample size to evaluate the efficacy of IV-NAC in the treatment of ALF in children was calculated. The original sample size was calculated assuming a one year survival rate for the patients in the treatment arm is 86.5% and 6 planned interim analyses. This comparison would need 92 patients in each arm (184 total) to achieve 80% power (likelihood of rejecting the hypothesis of equal survival rates) with a two-sided test of survival (log-rank test) at $\alpha=0.054$. The external Data and Safety Monitoring Board has accepted a revised interim monitoring plan for efficacy consisting of a single interim analysis when half of the sample of 184 reaches the one-year follow-up. Keeping the sample size at 184, this effectively lowers the type I error to 0.05 while maintaining 80% power.

Due to preliminary findings in a similar study, an additional interim analysis was performed. There will be 3 looks at the data; the first when 79 participants are enrolled (which was shown to the DSMB on August 30, 2007) among whom 42 participants were enrolled on or before July 1, 2006, i.e., enrolled for at least 1 year, the second when 92 participants reach the 1 year follow-up and the last when all 184 participants reach the 1 year follow-up.

With this revised plan, the power remains at 85%. The new O'Brien-Fleming boundaries will be:

- 4.550, 4.550 corresponding to a nominal α of 0.00005 at the first look
- 2.963, 2.963 corresponding to a nominal α of 0.00305 at the second look
- 1.969, 1.969 corresponding to a nominal α of 0.04900 at the third look

3.3.2 Endpoints of the study

Primary outcome measures:

1. Overall survival rate (spontaneous survival without transplant plus survival following transplantation) at one year following treatment allocation.

Secondary outcome measures:

1. Spontaneous survival (survival without transplantation)
2. Transplantation rate
3. Length of ICU and hospital stay
4. Number of organ systems failing:
 - a) Cardiovascular failure: defined as treatment with inotropic drugs: norepinephrine, epinephrine or dopamine (the latter $>5 \mu\text{g}/\text{kg}/\text{min}$), the terminal 24 h before death excluded.
 - b) Renal failure: defined as serum creatinine greater than 2 x the upper limit of normal for age and urine output less than 0.5 cc/kg/hour.
 - c) Intracranial hypertension: defined as intracranial pressure $> 25 \text{ mmHg}$ (if ICP monitored) or clinical signs of this condition (decerebrate posturing, abnormal pupillary reflexes).
 - d) Pulmonary support: defined as the need for mechanical ventilation for encephalopathy or respiratory failure, defined as an inspired oxygen fraction (FiO_2) above 0.40, the first 12 hours after intubation and the terminal 12 hours before death excluded. The FiO_2 criterion is important for the definition for two reasons: firstly, mechanical ventilation is used as a standard in the treatment of patients with cerebral edema to induce hyperventilation and thereby hypocapnia, and secondly, the medullary respiratory center may be depressed in patients with hepatic encephalopathy grade 4 and may thus cause a 'non-pulmonary' need for mechanical ventilation.
 - e) Infection: defined as detection of pathogenic microbial species in blood, tracheal, or urine cultures.
5. Degree of hepatic encephalopathy. The maximal hepatic coma grade (I - IV), and the number of days until recovery or death.

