 - d) Pulmonary support: defined as the need for mechanical ventilation for encephalopathy or respiratory failure, defined as an inspired oxygen fraction (FiO_2) above 0.40, the first 12 hours after intubation and the terminal 12 hours before death excluded. The FiO_2 criterion is important for the definition for two reasons: firstly, mechanical ventilation is used as a standard in the treatment of patients with cerebral edema to induce hyperventilation and thereby hypocapnia, and secondly, the medullary respiratory center may be depressed in patients with hepatic encephalopathy grade 4 and may thus cause a 'non-pulmonary' need for mechanical ventilation.
 - e) Infection: defined as detection of pathogenic microbial species in blood, tracheal, or urine cultures.
5. Degree of hepatic encephalopathy. The maximal hepatic coma grade (I - IV), and the number of days until recovery or death.

Therapy: Intravenous N-acetylcysteine

Total Duration of Therapy: 7 days. Duration may be less in the event of spontaneous recovery or liver transplantation.

Introduction

Acute liver failure (ALF) is a dramatic syndrome in which previously healthy individuals rapidly lose hepatic function due to a variety of causes, develop hepatic encephalopathy, and become critically ill within days [1, 2]. Even in the era of liver transplantation, many patients die either due to complications of this devastating disease or because of lack of available donor organs in a timely fashion [3]. Since ALF occurs relatively infrequently, no one center in the US has a large enough experience to conduct important clinical studies, either of natural history or treatment. The incidence of acute liver failure in children is unknown, but likely approaches 100 cases per year.

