3.2 Research Design and Methods

N-acetylcysteine is being tested in a double blind, placebo-controlled, randomized trial as a treatment for non-acetaminophen ALF in children. The study drug or placebo will be given as a 7 day continuous intravenous infusion to children with acute liver failure not due to acute acetaminophen toxicity.

Vials of NAC will be available at each clinical center in the research pharmacy. Upon identification of a patient, study personnel (investigator or coordinator) will obtain informed consent, and then notify the research pharmacist of the patient's body weight, coma grade, and age. Orders for the solutions and the informed consent will be submitted to the clinical center's pharmacy, confirming that the patient is part of the study and outlining the timing for the infusion. The pharmacist will then log onto a web-based treatment allocation system maintained at the DCC which assigns therapy using a minimization scheme designed to balance treatment groups within a site by age (less than 2 years vs. at least 2 years) and coma score (0,1 vs. 2-4). The research pharmacist will prepare either a NAC solution as outlined below or 5% dextrose (placebo). The N-acetylcysteine will be added to 5% dextrose. The solution containing N-acetylcysteine will be administered as a continuous infusion at a dose of 150 mg/kg bodyweight in 5% dextrose over 24-hours for 7

consecutive days. Volumes will be adjusted for small children. The solution will be delivered to the clinical center with study labels which do not disclose the specific contents. Patients allocated to placebo will receive volume-matched 5% dextrose infusions. The NAC solution is colorless, so there should be no difficulty with inadvertent product identification. It may be possible to identify the solution by its smell, but all reasonable efforts will be made to exclude investigators from awareness of this information. A standard order form for the infusions will be inserted in the patient's chart to provide uniform orders at the study onset. Infusion of the study solution should take place as soon as possible following study entry (consent signed).

Participation in the NAC trial will not interfere with standard treatment for ALF including liver transplantation, if it is considered appropriate.

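### The organ-failure count does not score dialysis as renal failure and, with no stated window or transplant rule, does not keep operative vasopressors out of cardiovascular failure

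*Protocol*

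**What the plan says.** The design synopsis and section 3.3.2 define secondary outcome 4, "Number of organ systems failing", in the same way, as five items (a) to (e). Three matter here.

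- Item (a): "Cardiovascular failure: defined as treatment with inotropic drugs: norepinephrine, epinephrine or dopamine". Dopamine carries a dose threshold; the other two drugs carry none. No indication or duration is given. The only period left out is "the terminal 24 h before death excluded".
- Item (b): "Renal failure: defined as serum creatinine greater than 2 x the upper limit of normal for age and urine output less than 0.5 cc/kg/hour". Both limits are required. Dialysis or renal replacement therapy appears nowhere in the protocol.
- Item (d): ventilation for encephalopathy or respiratory failure, with an FiO2 threshold of 0.40 and with "the first 12 hours after intubation and the terminal 12 hours before death excluded".

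No start or end of counting is stated, and no item refers to transplantation. On transplantation itself, section 3.2 says "Participation in the NAC trial will not interfere with standard treatment for ALF including liver transplantation". The synopsis says of the 7-day course "Duration may be less in the event of spontaneous recovery or liver transplantation". Section 3.3.1 plans on the basis that "while a greater percentage of children receive a liver transplantation (40%), 40% of these children die". The transplantation rate is a separate secondary outcome.

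**The concern.** Two features of the definitions can make the count record something other than organ failure.

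First, the items follow different logics. Items (a) and (d) treat the need for support as the failure. Item (b) ignores support and relies on two measurements, one of which dialysis lowers. Early dialysis can therefore remove the evidence that item (b) needs, and a child with severe renal failure can be scored as having none.

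Second, the authors removed periods in which support says little about organ function: the hours before death and, for ventilation, the hours after intubation. The transplant operation is a period of the same kind for item (a), and it was not removed. Children whose hypotension needs inotropic drugs, other than renal-dose dopamine, are excluded at entry (section 4.3, exclusion 8). Cardiovascular failure will therefore mostly be new after allocation, and drugs first given in theatre could be a material part of what item (a) records.

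To that extent the count would measure again whether a child was transplanted, while being read as evidence on multi-organ failure, which is part of the rationale in sections 2.1.2 and 2.1.5.

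**Working it through.** **1. The protocol's planning model.** Inputs from section 3.3.1 for placebo: 15% die without transplant, 40% are transplanted, and 40% of those die.

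- Spontaneous survival: 1 - 0.15 - 0.40 = 0.45
- Survival after transplant: 0.40 × (1 - 0.40) = 0.24
- Overall: 0.45 + 0.24 = 0.69, which is the stated 69%.

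The 40% transplant share is thus part of the model that produces the trial's planning figure. It corresponds to 0.40 × 92 = 36.8, about 37 of 92 placebo children.

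**2. Transplant share on NAC.** Section 6.2 gives 55.0% + 31.5% = 86.5% for the NAC arm. The diagram is not in the text available, so the transplant share has to be bounded:

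- Lower bound: every transplanted child survives, so 31.5% (0.315 × 92 = about 29).
- Upper bound: every child who is not a spontaneous survivor is transplanted, so 1 - 0.55 = 45% (0.45 × 92 = about 41).

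**3. Effect on item (a).** Let f be the fraction of transplanted children who score cardiovascular failure only because of drugs given for the operation. The documents do not give f. I assume it is the same in both arms and lies between 0.5 and 1.

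- Added to the placebo count: 0.40f organs per child
- Added to the NAC count: 0.315f to 0.45f
- Spurious difference, NAC minus placebo: (0.315 - 0.40)f to (0.45 - 0.40)f = -0.085f to +0.05f

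| f (assumed) | Added on placebo | Added on NAC | Spurious difference |
|---|---|---|---|
| 0.5 | 0.20 | 0.158 to 0.225 | -0.043 to +0.025 |
| 1 | 0.40 | 0.315 to 0.45 | -0.085 to +0.05 |

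The sign is not fixed. What enters both arms alike is larger than the difference between them, so dilution of the comparison is at least as much of a concern as bias.

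**4. Effect on item (b).** Here the argument is textual. The two limits are joined by *and*, with no alternative route to a score. A child started on dialysis while only one limit is met, and whose creatinine then stays at or below twice the upper limit of normal, never satisfies the item. A child who meets both limits together, before or during dialysis, still scores if failure is counted as ever present. The misclassified share is at most the share dialysed, which the protocol does not give.

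**The case against.** The strongest case on the other side has five parts.

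- **The window may be in the statistical analysis plan.** That plan is not shown, and a counting window for a secondary outcome is often placed there. A reader might infer from the protocol that counting runs through transplant surgery; the text says neither that it does nor that it stops. What stands is that the exclusions the protocol does fix leave transplant out. Nor would an unstated 7-day window cure this, since the synopsis foresees transplantation within the course.
- **The pulmonary item is largely protected.** The FiO2 threshold and the 12-hour rule filter out ventilation for the operation. A child still above 0.40 later may well have respiratory failure. I accept this; the transplant point is about item (a).
- **Counting regardless of transplant is defensible.** The primary outcome itself includes survival after transplant. Stopping the count at transplant would also shorten observation unequally, so that the arm with more or earlier transplants would show fewer failures. I accept this too, and the fix reflects it.
- **Both arms are scored by one rule under blinding.** True, but a common rule does not prevent a spurious difference when transplant rates differ.
- **Not every dialysed child is missed.** Correct; the claim is only that some can be.

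**Conclusion.** The renal point holds on the text: item (b) omits renal replacement therapy while items (a) and (d) are scored by support, so some dialysed children can be scored as free of renal failure. The number is unknown.

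The transplant point holds in a limited form: with no window and no transplant rule, operative norepinephrine or epinephrine is not kept out of item (a). Under the protocol's model the resulting arm difference is at most 0.085 organs per child in NAC's favour and 0.05 against it. This rests on an assumed f, equal in both arms, and on one-year transplant shares; transplants outside whatever window is used would reduce it.

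Three stronger readings are not supported:

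- That 20 to 40% of the placebo arm will score from surgery alone. This is 0.40 × 0.5 to 0.40 × 1.0, and it is an upper bound if 0.5 to 1 is taken as the rate of any operative vasopressor use, because some children will already have met item (a) before surgery.
- That the count will favour NAC through fewer transplants. The model allows more transplants on NAC than on placebo, and does not allow fewer than 31.5%.
- That all scored operative events follow the end of study drug. The synopsis says only that transplantation may shorten the course.

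This is a secondary outcome that should be tightened. The primary endpoint, sample size and error rates do not depend on it.

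**What to change.** In the synopsis and section 3.3.2:

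1. Add to endpoint definition (b): *or renal replacement therapy started for renal failure*.
2. State the counting window, and report organ failures arising before transplant separately from those first arising at or after the start of the operation. Show both alongside transplant and death by arm. This is preferable to only truncating the count at transplant, because the reader can then see how far each part drives a difference.

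Cost: a wording change, a split table, and one yes/no item on dialysis if the registry does not already hold it. Section 3.3.3 does not list transplant date among the trial's additional data, but the Cox model for transplantation in section 3.3.5 needs that timing. Section 6.3 describes daily assessment of intensive-care measures; whether each is held as a dated data field should be confirmed.

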32. Modig, J. and R. Sandin, *Haematological, physiological and survival data in a porcine model of adult respiratory distress syndrome induced by endotoxaemia. Effects of treatment with N-acetylcysteine*. Acta Chir Scand, 1988. **154**(3): p. 169-77.
33. Bailey, B. and M.A. McGuigan, *Management of anaphylactoid reactions to intravenous N-acetylcysteine*. Ann Emerg Med, 1998. **31**(6): p. 710-5.

NAC Study Protocol

6.2: Pediatric NAC Protocol

The overall survival rate at one year in this model is 69.0% (45.0% + 24.0%) in the placebo arm and 86.5% (55.0% + 31.5%). Estimating the total number of planned analyses at 6 using O'Brien Fleming boundaries for both H_0 and H_1 , a minimum of 184 patients (92 in each arm) will provide 80% power using a two-sided log-rank test (assuming proportional hazards) and an overall $\alpha = 0.054$ (if all 6 interim analyses are performed).

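### Secondary outcome 5 counts days to recovery or death on one scale, so its direction cannot be read when mortality differs between the arms

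*Protocol*

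**What the plan says.** The synopsis and Section 3.3.2 give the same definition for the fifth secondary outcome, degree of hepatic encephalopathy: "The maximal hepatic coma grade (I - IV), and the number of days until recovery or death". Section 1.0, which also lists the secondary endpoints, names only the highest degree of encephalopathy and no day count.

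The third secondary outcome is "Length of ICU and hospital stay", with nothing on how a stay that ends in death is counted. Elsewhere in the same list death is dealt with explicitly: for cardiovascular failure, "the terminal 24 h before death excluded", and a similar 12-hour exclusion applies to pulmonary support.

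Section 3.3.5 assigns Cox models to the primary outcome, spontaneous survival and transplantation. It names no method for the encephalopathy day count.

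The grade in outcome 5 runs from I to IV. Children without encephalopathy are eligible through the registry criteria (INR at least 2.0 or PT at least 20). Allocation in Section 3.2 uses grade 0 as a level, and the randomization checklist in Section 6.4 offers grade 0 as an entry.

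**The concern.** One number is used for two opposite events. A child who dies on day 3 scores 3, and a child who recovers on day 8 scores 8. If the count is read as a duration of illness, where fewer days is the natural good result, the death looks like the better outcome.

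The problem grows with the effect the trial hopes to show. The design assumes that NAC cuts one-year mortality by more than half, so death would truncate the count far more often on placebo than on NAC. A correct analysis of the variable as worded could then report slower recovery in the arm with more survivors, although recovery speed is the same in both. It could also report faster recovery that is equally an artefact.

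**Working it through.** **Planned mortality.** Section 3.3.1 states for placebo: "The one year death rate without transplant of 15% is lower than in the adult population", and then "while a greater percentage of children receive a liver transplantation (40%), 40% of these children die". Survival is 1 − 0.15 − 0.40 × 0.40 = 0.69. Section 6.2 gives the same 69.0% (45.0 + 24.0) for placebo and 86.5% (55.0 + 31.5) for treatment. One-year deaths are therefore 31% and 13.5%.

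**The plan's own sample size.** Section 3.3.1 says: "This comparison would need 92 patients in each arm (184 total) to achieve 80% power". HR = ln(0.865)/ln(0.69) = 0.391. Freedman's formula at two-sided 0.05 and 80% power gives (1.960 + 0.842)² × (1.391/0.609)² ≈ 41 events. The mean event rate is (0.31 + 0.135)/2 = 0.2225, so N = 41/0.2225 = 184.3. The stated 184 reproduces, so its mortality assumptions can be carried forward.

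**Expected day count.** Let p be the proportion dying, D the mean days to death and R the mean days to recovery, with D and R equal in both arms. The mean count is pD + (1 − p)R. The NAC minus placebo difference is (0.31 − 0.135)(R − D) = 0.175(R − D). Its sign is the sign of R − D. The protocol gives neither D nor R, so all day values below are assumed.

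**How often the test misleads.** Simulations used 92 per arm, gamma times with shape 2, two-sided Mann-Whitney at 0.05 and no drug effect on recovery speed (3,000 trials per row; ranges span repeat runs). Every child either dies or recovers; transplant and grade 0 are not modelled.

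| D, R (days) | Mean count, placebo vs NAC | Significantly against NAC | Significantly for NAC |
|---|---|---|---|
| 4, 10 | 8.1 vs 9.2 | 23.5% | 0.03–0.1% |
| 6, 12 | 10.1 vs 11.2 | 15.8–16.4% | 0.1–0.2% |
| 5, 8 | 7.1 vs 7.6 | 10.2–11.6% | 0.4% |

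Chance alone would give about 2.5% on each side.

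**Dependence on timing.** With R fixed at 14 days and the same mortality (1,500 trials per row):

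| D (days) | Mean count, placebo vs NAC | Against NAC | For NAC |
|---|---|---|---|
| 3 | 10.6 vs 12.5 | 42% | 0.1% |
| 5 | 11.2 vs 12.8 | 28% | 0.1% |
| 10 | 12.8 vs 13.5 | 6% | 0.8% |
| 14 | 14.0 vs 14.0 | 2.1% | 2.7% |
| 20 | 15.9 vs 14.8 | 0.4% | 7.1% |
| 28 | 18.3 vs 15.9 | 0.1% | 15.7% |

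A wider gap between death and recovery gives a larger bias. Equal timing removes it, and late deaths turn it in favour of NAC.

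**Which deaths are early.** The 31% and 13.5% are one-year deaths. On placebo, 16 of the 31 points (40% × 40%) follow transplantation, and 15 do not. The text does not give the NAC split. If a percentage T of NAC patients is transplanted, deaths without transplant are 45 − T. Since 31.5% survive after transplant, T lies between 31.5 and 45, so NAC deaths without transplant lie between 0 and 13.5%. Counting only deaths without transplant, over the three D, R pairs of the first table:

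| Early deaths, placebo vs NAC | Significantly against NAC |
|---|---|
| 15% vs 13.5% | about 3% |
| 15% vs 10% (T = 35) | 4–6% |
| 15% vs 5% (T = 40) | about 6–12% |
| 15% vs 0% (T = 45) | 9–18% |

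At 15% vs 10% the mean gap is only 0.05 × 3 = 0.15 to 0.05 × 6 = 0.30 days.

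**Same data, death scored worst.** In the D = 4, R = 10 scenario with 31% vs 13.5% deaths, days alive and free of encephalopathy to day 28 (death = 0) average 12.6 on placebo and 15.7 on NAC. Across the three pairs this measure is significant for NAC in about 50 to 54% of trials. Recovery speed is equal by construction, so all of that comes from mortality.

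**The case against.** The protocol lists the variable but assigns it no test and does not say that fewer days is better. The phrase may be shorthand for two durations reported separately, and a statistical analysis plan that is not at hand could split them or treat death as a competing event. That possibility stands. But the text as written defines one count with two ends, and a plan that followed it faithfully would inherit the fault.

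The objection on size also stands. A reader might take 10 to 24% as the expected error rate. It assumes that every one-year death falls in about the first week, while Section 3.3.1 places about half of the placebo deaths after transplant. Nothing says when those occur or whether encephalopathy had resolved by then.

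A reader might infer that the endpoint is always biased against the better arm. The documents do not support this: with no event times given, the bias could be absent or run the other way.

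A reader might also infer that length of stay contains the same stated error. The protocol only names that outcome, and a rule for deaths may properly sit in the analysis plan.

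Finally, a reader might infer that a child who never becomes encephalopathic has no score. Sections 3.2 and 6.4 both recognise grade 0, so this is a mismatch of labels that is easily put right.

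**Conclusion.** The point holds for the day count in secondary outcome 5. Its direction cannot be interpreted when mortality differs between arms, and that is a fault in the stated variable rather than a detail left for later.

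The size depends on assumptions. For mean death at 4 to 6 days and mean recovery at 8 to 12 days, a significant result against NAC occurs in about 10 to 24% of trials if all one-year deaths are early, and in about 4 to 12% if early deaths are 15% vs 5 to 10%. Other timings move these figures up or down, and deaths later than recoveries reverse the sign.

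Severity is moderate. The outcome is secondary and has no stated decision role. The primary log-rank comparison is unaffected, and survival would be reported beside it, so a real survival gain would remain visible.

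**What to change.** Separate the two events in the synopsis and Section 3.3.2. Either of these would do:

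- time to recovery from encephalopathy, with death as a competing event; or
- days alive and free of encephalopathy in a fixed window, with death scored worst.

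The second measure partly repeats the primary endpoint, because it moves with mortality; the first shows recovery more directly. Whichever is chosen, state how transplantation is counted, since 40% of placebo children are expected to receive one.

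Choose a window that the data cover. Section 3.3.3 describes a daily trial log and refers to registry data without listing them, so the sponsor should confirm that coma grade is recorded beyond the 7-day infusion.

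Score maximal coma grade 0 to IV and report it separately from the duration. If the analysis plan does not already handle deaths in length of stay, analyse that outcome in the same way, for example as days alive and out of ICU or out of hospital.

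The cost is a redefinition of secondary endpoints and a check of data coverage. Section 3.3.1 shows that 79 children were enrolled when an interim look went to the DSMB, so the change should be dated and documented as made without knowledge of results by arm. Comparability with raw durations in other reports is reduced, but those can still be tabulated descriptively.
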